#### Data discrepancies

- There were 58 patients in the OSU data that were not included in the Palarum data
- There were 48 patients in the Palarum data that were not included in the OSU data
- Total of 521 common patients between the 2 datasets

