HIPAA	Health Insurance Portability and Accountability Act of 1996
HUC	Health Pod Coordinator/UCA Monitor
ICF	Informed Consent Form
IEC	Independent Ethics Committee
IRB	Institutional Review Board
IRL	In Room Locator
IRT	In Room Tablet
PI	Principal Investigator
PLS	Palarum Local Server
PUP™	Patient is Up Fall Prevention System
RSSI	Receive Signal Strength Indicator
RTLS	Real Time Location System
PCS	Palarum Cloud Service
SAE	Serious Adverse Experience
WIRB	Western Institutional Review Board

PROTOCOL SYNOPSIS

TITLE	Testing the Effectiveness of a Fall Prevention System
SPONSOR	[name] PhD
FUNDING ORGANIZATION	Palarum, LLC
NUMBER OF SITES	1 Site on 3 floors of the Ohio State University Wexner Center Brain and Spine Hospital; (8 South, 9 South, 10 South, 8 East, 9 East & 10 East)
RATIONALE	
Each year, between 700,000 and 1,000,000 people in the United States fall in a healthcare environment (Agency for Healthcare Research and Quality, 2015). Falls can have a widespread and significant impact on health, can be deadly, and often result in high costs. Falls with serious injury are consistently among the Top 10 sentinel events reported to The Joint Commission's Sentinel Event database (The Joint Commission, 2015). The average 200-bed hospital might log 300 patient falls a year (based on 5 patient falls per 1000 patient days), which results in \$10,200 per fall in medical costs annually – or more than \$3 million. (Agency for Healthcare Research and Quality)
 
The best way to reduce the number of falls is to prevent them. A whole marketplace of bed and chair alerts and other devices has been developed to address the need, yet the numbers increase. On a busy patient floor, nurses lose valuable seconds just figuring out which patient's bed alert is sounding. We expect research to show that the Palarum PUP™ System reduces the incidence of falls.

STUDY DESIGN	Single arm trial
PRIMARY OBJECTIVE	To determine if the fall rate (as measured by falls per 1000 patient days) for patients designated “fall risk” decreases with the use of the intervention (Patient is UP fall prevention technology [PUP™]) when compared to historical NDNQI data for the prior 12 months (“Benchmark Data”) from nursing units where the intervention is being undertaken.

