7.6 Dispensing

All fall risk candidates who provide consent will be enrolled by the caregiver or CRC into the PUP™ Fall Risk Solution upon enrollment.

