## Palarum Data

### Primary dataset

- 732 entries with multiple enrollment and unenrollment dates (technical error)
- 569 patients after data cleaning multiple entries by limiting data to first enrollment and last unenrollment
- Variables included – floor, unit, enrollment date, unenrollment date. From these we calculated length of stay.

Variable	Level	Total (n=569)
OSU unit	Missing	3 (1%)
	10 East	127 (22%)
	10 South	108 (19%)
	8 East	64 (11%)
	8 South	102 (18%)
	9 East	81 (14%)
	9 South	84 (15%)
Length of Stay (Days)	Median [IQR] (min, max)	2 [1, 3.9] (0, 127.2)

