## Ohio State Data

### Admission Data

- 895 entries with multiple admission times, locations and diagnoses
- 585 patients after limiting to first entry per patient
- Variables included – admission time, department, room, diagnosis, date, date of birth height, weight. From these we calculated age and BMI. Unit, department, and room information were not useful – these were not from 8, 9, or 10 East and South which was inclusion criteria.

Variable	Level	Total (n=585)
BMI	Mean (SD) (min, max)	missing=29 30.8 (8) (14.9, 59.7)
Age	Mean (SD) (min, max)	59.5 (16.8) (18.1, 102.6)

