#### Study Objectives

- To determine if the fall rate (as measured by falls per 1000 patient days) for patients designated “high fall risk” decreases with the use of the intervention (Patient is Up fall prevention technology [PUP]) when compared to historical NDNQI data for the prior 12 months (“Benchmark Data”) from nursing units where the intervention is being undertaken.
  - We ran a one-sided one-sample test for Poisson means using fall events (0 falls) and length of stay (2211.6 days) to estimate the fall rate
  - Results are presented as the fall rate and the corresponding one-sided 90% confidence interval which provides an upper bound for the fall rate.
    - 0 falls (Upper bound 1.04) per 1000 days
  - This fall rate was lower than the historical rate of 4 falls per 1000 days
- To reduce the incidence of false alerts, <5%. Our goal is a high reliability notification system.
  - No data collected for this
- To provide positive alert reliability of 95%. Our goal is to reduce alert fatigue with nurses. To determine number of alerts sent out; what is the frequency of these patient safety events (i.e.), fall risk patient up, out of bed, unassisted
  - No data collected for this
- To gather compliance data and response times from alert to caregiver response.

- Stand Time captured in seconds

Variable	Level	Total (n=4999)
Stand (seconds)	Median (IQR) (min, max)	24.0 (5.0, 64.0) (1.0, 593.0)

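### Both parts of the primary fall rate come from Palarum records alone, so hospital-file patients without such a record (58 as stated, possibly far fewer net of mismatches) add no days and no falls to the 1.04 bound

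*SAP*

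**What the plan says.** **Source of the rate.** In the SAP (Primary dataset), length of stay is computed from Palarum enrolment and un-enrolment dates, for "569 patients after data cleaning multiple entries by limiting data to first enrollment and last unenrollment". Falls for the primary outcome come from the Palarum event file (SAP, Secondary dataset), which shows none. The test is described under Study Objectives: "We ran a one-sided one-sample test for Poisson means using fall events (0 falls) and length of stay (2211.6 days) to estimate the fall rate". The reported one-sided 90% upper bound is 1.04 per 1000 days.

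**Unmatched patients.** The hospital file holds "585 patients after limiting to first entry per patient". Under Data discrepancies the SAP states "There were 58 patients in the OSU data that were not included in the Palarum data", then "There were 48 patients in the Palarum data that were not included in the OSU data", and gives a "Total of 521 common patients between the 2 datasets". It offers no reason for either mismatch and describes no step that adds anyone back.

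**What the protocol planned.** Section 7.6 says "All fall risk candidates who provide consent will be enrolled by the caregiver or CRC into the PUP™ Fall Risk Solution upon enrollment". Section 13.2 counts patient days from the start of the PUP System until discharge or removal from the fall risk protocol. The synopsis (Method of Use) has every fall reported through the hospital's own process, independently of the Palarum system. The comparison rate is historical: the primary objective speaks of a fall rate "when compared to historical NDNQI data for the prior 12 months (“Benchmark Data”) from nursing units where the intervention is being undertaken".

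**The concern.** Because numerator and denominator share one source, a patient without a Palarum record is absent from the primary result altogether. Under section 7.6 a consenting patient should have such a record, so its absence needs explaining. A patient who was monitored but whose record was lost is inside the section 13.2 definition, and a fall by that patient should count. The hospital reporting route in the synopsis would have captured it, but the SAP does not use that route. Its hospital Falls Data are entries on history of falling, not falls during the study.

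The benchmark comes from the nursing units in the 12 months before the study, so it cannot depend on a Palarum record. At stake are the zero rate and the 1.04 bound, both of which may be read as describing everyone who received the intervention.

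**Working it through.** **Inputs.** SAP: 0 falls; 2211.6 days; 569 Palarum patients; 585 hospital-file patients; 521 in both; 58 and 48 unmatched. Protocol 13.2: historical rate 0.004 per day, one-sided alpha 0.1. I take the 2211.6 days to belong to the 569 patients. The SAP does not say so outright, but patients with no Palarum record are excluded on any reading.

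**Reported bound.** The exact Poisson upper bound is χ²(0.90; 2x + 2) / (2T). With x = 0 this is −ln(0.1)/T = 2.3026/2211.6 = 1.041 per 1000 days, which reproduces 1.04. The exact p-value is exp(−0.004 × 2211.6) = exp(−8.846) = 0.00014.

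**How many are left out.**
- Palarum side: 569 − 48 = 521, which agrees with the stated overlap.
- Hospital side: 585 − 58 = 527, which does not. By subtraction, 585 − 521 = 64 are unmatched.
- Share of the hospital file: 58/585 = 9.9%, or 64/585 = 10.9%.
- If all 48 unmatched Palarum patients are hospital-file patients under another identifier, they are already counted. The net omission is then 58 − 48 = 10 on the stated counts, or 585 − 569 = 16 on the file totals.

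**Effect on the result.** The documents give no stay for these patients. I assume the Palarum mean, 2211.6/569 = 3.89 days. For n added patients, T = 2211.6 + 3.887n.

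| Patients added | Total days | Bound per 1000 days, 0 falls added | 1 fall | 2 falls | 3 falls | p, 5 falls | p, 6 falls |
|---|---|---|---|---|---|---|---|
| 10 | 2250.5 | 1.02 | 1.73 | 2.36 | 2.97 | 0.116 | 0.207 |
| 16 | 2273.8 | 1.01 | 1.71 | 2.34 | 2.94 | 0.110 | 0.198 |
| 58 | 2437.0 | 0.94 | 1.60 | 2.18 | 2.74 | 0.077 | 0.147 |
| 64 | 2460.4 | 0.94 | 1.58 | 2.16 | 2.72 | 0.073 | 0.140 |

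The p-value is P(X ≤ x) for a Poisson mean of 0.004T. Four added falls remain significant in every row (largest p = 0.055). Significance is lost at 5 falls if 10 or 16 patients are added, and at 6 if 58 or 64 are. If the 58 stayed only one day each (2269.6 days), it is lost at 5 (p = 0.111).

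**Plausibility.** At the historical rate, 58 patients contribute 58 × 3.887 × 0.004 = 0.90 expected falls. The chance of at least one is 1 − exp(−0.90) = 59%; the chance of six or more is about 0.0003. So at that rate a changed bound is quite possible, and a reversed test is not.

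**The case against.** The strongest reply is that the gap may be largely a linkage problem. Patients are unmatched in both directions, and caregivers key in the name, initials or record number at enrolment (Protocol 4.2 and 9.2), so mismatched identifiers are a natural explanation. This stands: 58 is not a floor for the number left out.

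That all 58 are study patients is also an inference. SAP Admission Data says the unit fields in the hospital file were not from the study units, and nowhere does the SAP say these patients were consented or registered. This stands too, and is a reason to resolve each case.

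Third, section 13.2 counts days from PUP initiation, so a patient never fitted adds no planned exposure. That is correct. The plan is departed from only for patients who started and whose records are missing, and their number is unknown. It does not support making all consented patients the primary set.

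Stronger readings that a reader might infer, and that the documents do not support:
- *Records are known to have been lost.* The technical error in the SAP's Primary dataset refers to multiple enrolment and un-enrolment dates, that is, surplus entries.
- *One uncounted fall pushes the test's error rate above 10%.* A cut-off of five falls gives 12.5% only if the omitted patients' falls are added without their days (mean 8.846). With the days of 58 patients included (mean 9.748) it is 7.7%.
- *The rate is shown to be biased low.* No document shows that any of these patients fell, and with no falls among them the bound improves. Nor do the documents describe the benchmark's patient mix beyond units and period.

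Finally, the gap is wider than these patients: no hospital-reported study falls are used for anyone, including the 521 matched. That is true, and the same record linkage would serve both.

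**Conclusion.** The concern holds as an unexplained exclusion from the primary rate. The SAP discloses the mismatch but neither explains it nor carries it into the result. The number omitted lies between about 10 to 16 and 58 to 64. The test conclusion is barely exposed, since about 5 to 6 falls would be needed against 0.9 expected among 58 patients at the historical rate. The zero rate and the 1.04 bound are exposed: a single fall would move the bound to about 1.6 to 1.7 per 1000 days. These figures rest on the assumed mean stay of 3.89 days and on the omitted patients having started the system. Whether any of them did so, or fell, cannot be settled from the documents.

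**What to change.** 1. Reconcile the 58 (or 64) and the 48 by identifier, correct the counts so that they agree with 521, and record the reason for each missing Palarum record.
2. Keep the section 13.2 definition, days from PUP initiation, for the primary analysis. Add back every patient who started the system but has no Palarum record, with dates from the hospital record and falls from the hospital's fall reports.
3. Report a sensitivity row for all registered patients, including any never fitted, with the test and the one-sided 90% upper bound.
4. Until this is done, state beside the 1.04 bound that it applies only to patients with a Palarum record.

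The cost is a record lookup for about 60 patients, an identifier check of the 48, one added analysis row and some SAP wording. The sensitivity row will include some days without the device, and the bound may become less favourable.

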#### Study Objectives

- To determine if the fall rate (as measured by falls per 1000 patient days) for patients designated “high fall risk” decreases with the use of the intervention (Patient is Up fall prevention technology [PUP]) when compared to historical NDNQI data for the prior 12 months (“Benchmark Data”) from nursing units where the intervention is being undertaken.
  - We ran a one-sided one-sample test for Poisson means using fall events (0 falls) and length of stay (2211.6 days) to estimate the fall rate
  - Results are presented as the fall rate and the corresponding one-sided 90% confidence interval which provides an upper bound for the fall rate.
    - 0 falls (Upper bound 1.04) per 1000 days
  - This fall rate was lower than the historical rate of 4 falls per 1000 days
- To reduce the incidence of false alerts, <5%. Our goal is a high reliability notification system.
  - No data collected for this
- To provide positive alert reliability of 95%. Our goal is to reduce alert fatigue with nurses. To determine number of alerts sent out; what is the frequency of these patient safety events (i.e.), fall risk patient up, out of bed, unassisted
  - No data collected for this
- To gather compliance data and response times from alert to caregiver response.

- Stand Time captured in seconds

Variable	Level	Total (n=4999)
Stand (seconds)	Median (IQR) (min, max)	24.0 (5.0, 64.0) (1.0, 593.0)
